6.3.3.3 Dose modifications for non-hematological toxicity

Table 1-2 summarizes the recommendations for dose delays and modifications for all non-hematological adverse events.

Table 1-2: Non-hematological Criteria for Dose Delay and Dose Modification of temsirolimus/placebo			
Grade	Dose Delay	Dose Modification	
Grade 0-2	Treat on time	No Change ^b	
Grade 3 and 4	DELAY ^a until ≤ Grade 2	DECREASE one dose level ^c	
If the same grade 3/4 non- hematological toxicity reoccurs after first reduction	Discuss treatment discontinuation with coordinating investigator		

- a. If no recovery after 30 days delay, treatment will be discontinued
- b. If ≤ grade 2 toxicity occurs after the first two cycles of maintenance therapy, the dose will be increased by one dose level to a maximum dose of 25 mg. If during the following two maintenance cycles still no grade 3 or 4 toxicity occurs, another dose escalation up to 25mg can be considered.
- c. If a dose reduction below dose level -2 is required, treatment will be discontinued

These recommendations apply, if the adverse event is considered to be related to temsirolimus, but not to the chemotherapy.

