6.2.4 Overlapping toxicities of temsirolimus and standard cytotoxic therapy

Potential overlapping toxicities of temsirolimus and standard cytotoxic therapy include:

- Increased severity and duration of hematological toxicity, including anemia, thrombocytopenia and leukopenia
- Increased risk or severity of nephrotoxicity

• Further non-hematological overlapping toxicities cannot be ruled out

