6.2.5 Dose reduction in standard cytotoxic therapy

In principle, dose reduction of standard cytotoxic therapy is not permitted in this study – with the exception of individual cases in the best interest of the patient. In case that overlapping toxicities of standard cytotoxic treatment and temsirolimus should require a dose reduction, the dose of temsirolimus must be reduced (for dose modification and delay see 6.3.3).

If individual cases of severe toxicities should require an additional dose reduction of standard cytotoxic therapy, the coordinating investigator should first be consulted, if possible, before dose reduction. Dose reduction and reason for dose reduction should be documented. Depending on the toxicities and dose modification, the patient might be withdrawn from the study.

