6.3.3.1 General dose modifications

If a dose reduction at dose level -3 is required, the patient should be permanently discontinued from the study treatment.

As a general rule, grade 3 toxicity should be followed by permanent dose reduction of temsirolimus during that therapy phase (chemotherapy phase or maintenance phase). If a grade 3 toxicity during the chemotherapy phase resolves after dose reduction of temsirolimus, the dosage of temsirolimus may be re-escalated after two cycles of maintenance therapy if \leq grade 2 toxicity occurs after the first two cycles of maintenance therapy. If during the following two maintenance cycles still no grade 3 or 4 toxicity occurs, another dose escalation up to 25mg can be considered.

Resolution of an adverse event is defined as disappearance or reduction of the adverse event to < grade 3 toxicity. For patients with grade 2 or greater toxicities present at baseline resolution to at least baseline levels will apply.

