These recommendations apply, if the adverse event is considered to be probably related to temsirolimus treatment but not to the chemotherapy. The dose of temsirolimus will be reduced according to the following scheme:

initial dose (starting dose)	25 mg abs.
Dose level -1:	20 mg abs.
Dose level -2:	15 mg abs.
Dose level -3:	Discontinue from study

Reduced dose levels will be maintained throughout the chemotherapy phase and the first two maintenance phase cycles.

If patients with reduced temsirolimus dose do not experience any grade 3 or grade 4 toxicity during the first two maintenance phase cycles, the temsirolimus dose will be escalated at one dose level. If during the following two maintenance cycles still no grade 3 or 4 toxicity occurs, another dose escalation up to 25mg can be considered.

Key inclusion and exclusion criteria

Kev inclusion criteria

- Patients with newly diagnosed AML (except APL) according to the FAB classification, including AML evolving from MDS or other hematological diseases and AML after previous cytotoxic therapy or radiation (secondary AML).
- Bone marrow aspirate or biopsy must contain ≥ 20% blasts of all nucleated cells or differential blood count must contain ≥ 20% blasts. In AML FAB M6 ≥ 30% of non-erythroid cells in the bone marrow must be leukemic blasts. In AML defined by cytogenetic aberrations the proportion of blasts may be < 20%.
- Age \geq 61 years
- Informed consent, personally signed and dated to participate in the study
- Willingness of male patients whose sexual partners are women of child-bearing potential (WOCBP), to use an effective form of contraception (pearl index < 1%) during the study and at least 6 months thereafter.

Effective forms of contraception are complete sexual abstinence, combined oral contraceptive, hormone IUCD, vaginal hormone ring, transdermal contraceptive patch, contraceptive implant or depot contraceptive injection in combination with a second method of contraception like a condom or a cervical cap / diaphragm with spermicide or surgical sterilisation (vasectomy) in male patients. WOCBP are defined as sexually mature women who have not undergone a hysterectomy or surgical sterilization or who have not been naturally postmenopausal for at least 12 consecutive months (i.e., who has had menses any time in the preceding 12 consecutive months).

Key exclusion criteria

- Patients who are not eligible for standard chemotherapy as described in chapter 6.2

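### Section 6.2.5 sends overlapping toxicity to 6.3.3 for dose reduction and delay, but 6.3.3.3 excludes events also attributed to chemotherapy, so the hold, 30-day stop and recurrence rules fall away

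*Protocol*

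**What the plan says.** Section 6.2.4 of the protocol expects the toxicities of temsirolimus and the chemotherapy to overlap outside the blood count. It lists "Increased risk or severity of nephrotoxicity" and adds "Further non-hematological overlapping toxicities cannot be ruled out".

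Section 6.2.5 gives the rule for that case: "In case that overlapping toxicities of standard cytotoxic treatment and temsirolimus should require a dose reduction, the dose of temsirolimus must be reduced". A parenthesis at the end of that sentence points to 6.3.3 for modification and for delay.

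Section 6.3.3 sets the dose steps: 25, 20 and 15 mg, then discontinuation. Section 6.3.3.1 adds a rule with no attribution condition: "As a general rule, grade 3 toxicity should be followed by permanent dose reduction of temsirolimus during that therapy phase".

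Section 6.3.3.3 introduces Table 1-2 as covering all adverse events of the non-hematological kind. For grade 3 and 4 the table holds treatment until grade 2 or less and lowers the dose by one level. Its first footnote reads "If no recovery after 30 days delay, treatment will be discontinued". If the same toxicity recurs after the first reduction, the instruction is "Discuss treatment discontinuation with coordinating investigator". The section then closes with "These recommendations apply, if the adverse event is considered to be related to temsirolimus, but not to the chemotherapy".

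The corresponding sentence in the synopsis (section 14) is "These recommendations apply, if the adverse event is considered to be probably related to temsirolimus treatment but not to the chemotherapy".

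**The concern.** The section written for overlapping toxicity refers sites to a table whose closing sentence excludes overlapping toxicity. That sentence also contradicts the opening of its own section.

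The case is foreseeable. During induction and consolidation, temsirolimus or placebo is always given around chemotherapy, on days -1 and 8 (6.3.2.2, 6.3.2.4, 6.3.2.6). In the first induction, day 8 directly follows cytarabine on days 1 to 7 and daunorubicin on days 3 to 5. If a grade 3 or 4 renal event has appeared by then and the investigator attributes it to both treatments, the protocol does not say whether to hold the day 8 dose, how long to wait before stopping, or whom to call if the event returns. Investigators are blinded in this phase (5.3.3). Sections 8.5 and 11.1 also concede that a possible relation to study drug will often be hard or impossible to judge. A condition that requires attribution to temsirolimus and not to chemotherapy is hardest to apply in exactly this setting.

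What is at stake is consistent safety management of patients aged 61 or over. The efficacy analysis is not at stake.

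**Working it through.** No arithmetic applies. The check sets the provisions side by side for one case: a grade 3 or 4 non-hematological event attributed to both temsirolimus and chemotherapy.

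| Provision | Where it stands | Applies to the shared event, read literally? |
|---|---|---|
| Reduce temsirolimus | 6.2.5 | Yes, when the toxicity calls for a reduction; no grade is set |
| Reduce after grade 3 | 6.3.3.1 | Yes; no attribution condition, but grade 4 is not named |
| Steps of 25, 20, 15 mg, then stop | 6.3.3 and 6.3.3.1 | Yes |
| Hold until grade 2 or less | Table 1-2 | No, excluded by the closing sentence |
| Stop after 30 days without recovery | Table 1-2, footnote a | No, same reason |
| Discuss stopping if it recurs | Table 1-2, last row | No, same reason |

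1. *Could another section supply the three missing rules?* Section 6.3.3.1 covers reduction, re-escalation and discontinuation at level -3. It has no hold, no time limit and no recurrence step. Section 6.3.3.2 and Table 1-1 are hematological only. The synopsis repeats the exclusion. So nothing else in 6.3.3 fills the gap.

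2. *Does 6.2.5 stand alone?* No. It refers to 6.3.3 for delay, and the only non-hematological delay rule there is the one that excludes the event.

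3. *Is the exclusion used consistently?* No. The definition of dose-limiting toxicity in 6.3.1 counts grade 3 non-hematological events related to temsirolimus without excluding those also due to chemotherapy. In the run-in part, a shared event can therefore count as dose-limiting yet fall outside Table 1-2.

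4. *Which attribution threshold applies?* The body asks for a relation, the synopsis for a probable one. Section 8.4 records adverse events only as related or unrelated to temsirolimus. Graded scales that include a probable level appear in 8.5 and 8.7, for serious events. For a non-serious event, the synopsis threshold has no matching recorded item. This is a secondary point.

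5. *Can the frequency be sized?* Not from the protocol. Section 8.12.1.1 lists elevated creatinine at above 30% and acute renal failure as rare, while the table in 8.12.1.2 puts increased creatinine in the band from above 1% to 10%. Neither figure is for grade 3 or 4, and neither concerns attribution to both drugs.

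**The case against.** The strongest reply is that the text can be read coherently. Table 1-2 opens as covering all such events, 6.2.5 is the specific rule for overlap and imports 6.3.3 for delay, and the closing sentence is then meant to remove only events that belong to the chemotherapy. That may well have been the intent. The closing sentence does not say so: an event related to both treatments is not one unrelated to chemotherapy, and the synopsis repeats the exclusion.

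Second, other safeguards narrow the gap, and this stands:
- Consolidation may be postponed by up to 4 weeks (6.3.2.5), and its day -1 dose moves with it.
- Maintenance contains no chemotherapy and starts no earlier than day 28 of the last cycle, so shared attribution is much less likely there.
- The investigator may withdraw a patient for safety at any time (5.4), and drug-related toxicity is a reason for removal (7.6.1).
- If the chemotherapy must also be reduced, 6.2.5 already asks for the coordinating investigator to be consulted where possible.

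What remains is mainly the day 8 dose within a cycle and the recurrence step.

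Third, excluding chemotherapy-attributed events might be a deliberate way to protect temsirolimus dose intensity. That does not fit 6.2.5, which already makes temsirolimus the drug to reduce when toxicities overlap.

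A reader might go further and infer that shared events have no reduction rule at all, or that sites are told to give the full dose on time. The documents support neither. Reduction survives through 6.2.5, the steps in 6.3.3 and, for grade 3, section 6.3.3.1, and no text orders full dosing for these events.

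**Conclusion.** The contradiction is real and can be read directly from the text. For a grade 3/4 non-hematological event attributed to both drugs, three provisions are lost: the hold until grade 2 or less, the 30-day stop and the recurrence discussion. The reduction itself is not lost. The practical weight falls on the day 8 dose in induction and consolidation cycles.

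This rests on reading the closing sentence of 6.3.3.3 as written and on shared attribution occurring, which 6.2.4 foresees but does not quantify. No claim is made about how often it occurs or about cumulative exposure. Hematological toxicity, governed by 6.3.3.2, is outside the point. A reader might also suspect an effect on the primary analysis. There is none: patients stay in their randomized arm whatever dose they receive, so the intention-to-treat test of event-free survival remains valid. This is a safety instruction worth correcting, not a threat to the trial's conclusions.

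**What to change.** Replace the closing sentence of 6.3.3.3 and its counterpart in the synopsis with identical text, for example:

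*This table applies to any adverse event judged related to temsirolimus, whether or not it is also attributed to the chemotherapy. It does not apply to events attributed to the chemotherapy alone.*

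This brings 6.3.3.3 into line with 6.2.5 and with its own opening, and removes the second threshold from the synopsis. Attribution can use the related/unrelated item already recorded under 8.4.

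Leave the reduction rule in 6.3.3.1 in place for non-hematological toxicity. It is the only reduction rule within 6.3.3 that covers such toxicity without an attribution condition, and tying it to 6.3.3.3 would remove a safeguard.

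The cost is two sentences through the amendment route in 10.1, with no change to forms, visits, endpoints or sample size. The downside is somewhat more holds and reductions of study drug. Some will fall on placebo patients, because attribution during chemotherapy is made blind. The protocol gives no basis for quantifying that increase.

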6.4 Concomitant medications / therapy

Hydroxyurea may be used according to the centers' standard practice to decrease initial leukocytosis before starting with temsirolimus/placebo on day -1 of the first induction therapy cycle.

Leukocytapheresis is not contraindicated in this study and may be an option to decrease elevated leukocyte counts (i.e., leukocytes > 100,000/µl and/or leukostatic syndrome).

All appropriate and supportive care for disease-related symptoms will be provided to all patients. Sufficient anti-emetic prophylaxis is required prior to the administration of standard chemotherapy and temsirolimus according to the study centers' standard procedures. Symptomatic treatments should be used as needed and may be given as prophylactics in subsequent cycles. This should include sufficient hydration, alkaline treatment (i.e. Uralyt® or other) and prophylactic treatment with allopurinol in order to prevent occurrence of tumor lysis syndrome.

As allergic/hypersensitivity reactions may occur in patients receiving temsirolimus, an H₁ antihistamine should be administered to patients before the start of the intravenous temsirolimus infusion.

Anti-microbial prophylaxis including antifungal prophylaxis in the presence of myelosuppression should be given according to the study centers' standard procedures. In addition, according to common practice, a pneumocystis jirovecii prophylaxis should be conducted with pentamidine inhalations 300 mg every 4 weeks from the first week of induction therapy until the end of consolidation therapy. Weekly monitoring of CMVpp65 antigen or CMV DNA qualification in case of severe leucopenia is recommended until the end of the maintenance therapy and pre-emptive therapy will be started in case of positive results.

It is optional to give G-CSF or Pegfilgrastim to patients during the treatment course according to the study center practices regarding the use of growth factors. If G-CSF or Pegfilgrastim is used, it should be given after confirmation of adequate blast clearance after the first course of induction therapy, on day 10 of the second course of chemotherapy (two days after the end of the last cytarabine infusion) and on day 7 of consolidation therapy (two days after the end of the last cytarabine infusion).

Furthermore, it is to the discretion of the participating centers, which type of G-CSF preparation they choose to treat their patients. Available preparations include filgrastrim (Neupogen®), lenograstrim (Granocyte®) and the pegylated form pegfilgrastrim (Neulasta®).

Possible drug interactions as described in Section 6.1.3 should be considered.

7 STUDY PROCEDURES

7.1 Study evaluations

Diagnostic procedures follow the general standard of good clinical practice for the diagnosis and treatment monitoring of AML patients.

7.1.1 Evaluations before study inclusion (screening) and treatment

- Complete blood count (CBC) with differential and platelets
- Serum chemistries: electrolytes, calculated creatinine, urea, uric acid, bilirubin, AP, AST and / or ALT, LDH, lipase, cholesterol, triglycerides, glucose, phosphate
- Coagulation: PTT, quick, fibrinogen, ATIII
- Urine analysis
- Blood type
- Full history and clinical examination
- Vital signs
- · Body height and body weight
- Performance status (ECOG)
- ECG
- Echocardiography or MUGA scan⁴
- Ultrasound of the abdomen
- Lung function test
- Bone marrow biopsy
- Bone marrow aspirate or peripheral blood:
 - Cytomorphological examination incl. cytochemistry
 - Immunophenotyping
 - Cytogenetics

 Molecular genetic analyses for the presence of Flt3-ITD, genomic ratio of the presence of Flt3-ITD vs. Flt3-WT, for NPM1 mutations and for the presence of BCR-ABL, PML-RARα, AML1-ETO and CBFβ-MYH11 translocation products

- Asservation of bone marrow and peripheral blood cells (Ficoll-treated) in a central tissue repository⁵

⁴ The same method for determination of the left ventricular function should be used for each patient throughout the study participation

The material from the central tissue repository will be used for exploratory research purposes. These analyses are optional and will not be part of the medical report of this trial

7.1.2 Evaluations on day 1 of 1st induction chemotherapy cycle (i.e. after temsirolimus/placebo and before the first administration of cytarabine)

(for full details about evaluations please refer to 7.2)

- Complete blood count (CBC) with differential and platelets
- Asservation of 10ml heparinized peripheral blood (Ficoll-treated cells) in a central tissue repository⁵

7.1.3 Evaluations during further treatment

(for full details about evaluations please refer to 7.2)

- Complete blood count (CBC) with differential and platelets
- Bone marrow aspirate (cytomorphology, immunophenotyping, cytogenetics, molecular genetics)
- Asservation of bone marrow and peripheral blood cells (Ficoll-treated) in a central tissue repository (only bone marrow or peripheral blood remaining after standard diagnostics)⁵.
- Control of CBC (with differential and platelets), coagulation and serum chemistries (including creatinine)
- Performance status (ECOG)
- Physical examination
- · Body weight
- Diagnostic procedures i.e. in case of severe infections will follow standard procedures
- Evaluations performed before the first course of induction therapy will be repeated prior to each following course if necessary in the investigator's opinion
- ECG and echocardiography / MUGA scan⁴ as often as necessary in the investigator's opinion
- Lung function test as often as necessary in the investigator's opinion

7.1.4 Evaluations at the end of maintenance therapy

(for full details about evaluations please refer to 7.2)

- Performance status
- Physical examination
- · Vital signs

• CBC (with differential and platelets), coagulation and serum chemistries Urine pH

⁴ The same method for determination of the left ventricular function should be used for each patient throughout the study participation

The material from the central tissue repository will be used for exploratory research purposes. These analyses are optional and will not be part of the medical report of this trial.

- Bone marrow aspirate
- Asservation of vital bone marrow cells (Ficoll-treated bone marrow), bone marrow RNA,
 DNA and protein lysates, serum and plasma in a central tissue repository (remaining material after completion of standard diagnostic procedures)⁵
- Lung function test

7.1.5 Evaluations in suspected case of relapse

- CBC (with differential and platelets)
- Bone marrow aspirate
- Asservation of vital bone marrow cells (Ficoll-treated bone marrow), bone marrow RNA,
 DNA and protein lysates, serum and plasma in a central tissue repository (remaining material after completion of standard diagnostic procedures)⁵

7.1.6 Evaluations during follow up (standard routine parameters)

In case of relapse, study exclusion or refusal of informed consent, patients should be followed until one year after the start of the induction therapy. These follow-up evaluations include:

- Bone marrow aspirate in case of suspected relapse
- CBC with differential monthly
- Performance status (ECOG) monthly
- All other follow-up investigations according to general standards and according to the investigator's decision

Study protocol, TOR-AML, Final Version 3.1, April 13rd, 2012

40

⁵ The material from the central tissue repository will be used for exploratory research purposes. These analyses are optional and will not be part of the medical report of this trial.

7.2 Schedule of evaluations

	Within 10 days prior to 1st course of 1st induction therapy	Day 1 of 1st induction therapy before the first administration of cytarabine	During and between induction therapy until hematological recovery	d 15 ± 2	Before 2nd course of induction therapy (if applicable)	d 35-42 after last course of induction	Before 1st course of consolidation therapy	Before 2nd course of consolidation therapy	Start of maintenance therapy	During maintenance therapy or observation	End of maintenance therapy	Follow –up: until one year after 1st induction therapy	Suspected relapse (during study treatment or follow-up)
Informed consent	Х												
Medical history	Х												
Performance status and physical examination ^a	Х				Х	(X)	Х	Х	Х	weekly	Х	Х	
Vital Signs (blood pressure and pulse) ^a	Х				Х	(X)	X	x	X	weekly	x		
Body weight and height ^a	Х				Х		Х	Х					
CBC (with differential and platelets) ^a	×	Xc	Once weekly		x	×	×	×	x	weekly	×	×	Xe
Chemistry, including liver function, cholesterol, triglycerides, glucose, creatinine, phosphate, coagulation ^a	X		Once weekly		X	(X)	Х	x	X	weekly	x		
Urinalysis ^a	Х												
ECG and echocardiography / MUGA scan ^{b,g}	Х												
Ultrasound of the abdomen ^a	X												
Lung function test ^a	Х						X				X		
Assessment of AE and relevant CoMed			After each cycle during induction/consolidation and monthly during maintenance										
Bone marrow (BM) aspirate	Х			Х			Х	Х	X ^d	X ^d	Х	Х	Xe
BM biopsy	х												
BM / PB for cell repository	Х	X ^f											

^a In addition, these evaluations should be repeated as often as necessary in the opinion of the treating physician

^b The same method for determination of the left ventricular function should be used for each patient throughout the study participation

^c Material for differential CBC may be stored and analyzed on the next working day

^d At suspected relapse

^e For patients with suspected or confirmed relapse. For patients with neutrophils $< 1,000/\mu l$ or platelets $< 75,000/\mu l \ge 30$ days after start (day 1) of the last induction therapy or of a consolidation therapy cycle, these evaluations will be performed between day 30 and 35

f 10ml of heparinized peripheral blood only (after temsirolimus/placebo; before start of induction chemotherapy)

^g These evaluations should be repeated as often as necessary in the opinion of the treating physician, especially in patients with a history of heart disease or when a heart disease or cardiotoxicity is clinically suspected

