5 SELECTION, RANDOMIZATION AND WITHDRAWAL OF PATIENTS

5.1 Number of patients

For the run-in part, accrual of 12 (up to 18) patients is planned (see chapter 6.3.1). According to the power calculations given in section 9.1, n = 200 patients will be included in the main (controlled) part of the study with an equal allocation rate to both treatment arms.

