7.4 Duration of the study

Accrual time: 24 months F	Follow-up period ^a : 12 months
---------------------------	---

^a In case of a relapse / treatment failure, a study exclusion or a refusal of informed consent, the patients overall survival will be followed up until one year after the start of the first induction cycle.

Assuming an accrual time of 24 months and a duration of follow-up (of the last included patient) of approximately 12 months, the total duration of the study will be approximately 48 months.

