9 STUDY OUTCOME AND STATISTICAL ANALYSIS

9.1 Power and Sample Size Calculation

A single stage design with fixed sample size was chosen. The accrual time will be 24 months with a follow-up time of 12 months (see 7.4).

Let m_0 and m_1 be the median event free survival times for the control and the temsirolimus arm respectively. The Logrank test will be used to test the null hypothesis

 $H_0: m_1/m_0 = 1$

against the two-sided alternative

 H_1 : $m_1/m_0 \neq 1$.

The allocation ratio was determined to be $n_1/n_0 = 1.0$.

A total of 146 evaluable patients are expected to be sufficient to detect a prolongation of the median EFS from 7 to 11.75 months with a power of 80% and a significance level of α =0.05. This change is considered to be clinically relevant. Under the assumption of loss to follow-up, or of alternate post-remission treatment (i.e. bone marrow transplantation), or protocol violation in up to 54 patients, total accrual to the phase II part of this trial is planned for 200 patients (100 per arm).

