9.2 Statistical Analysis Plan

The statistical analysis will be performed according to the intention to treat principle (ITT analysis). This means that every patient included into the study and randomized to one treatment arm will be evaluated in that arm, even if he does not receive study-medication, or if any other violations of the study protocol occur.

- The primary endpoint (median EFS) will be compared between both treatment arms using two-sided stratified Logrank test. This part of the analysis is considered as confirmatory.
- Analyses of secondary endpoints will include, among others, relapse free survival, early
 response rate, morphologic and molecular CR-rate, overall survival, minimal residual
 disease, evaluation of potential biomarkers indicating the course of disease, including
 genetic, epigenetic, transcriptional and protein markers as well as indicators of autophagy
 in leukemic blasts, bone marrow, peripheral blood cells, serum and plasma
- Patients undergoing allogenic bone marrow transplantation are censored for EFS and OS at the time of bone marrow transplantation.

• In addition to the ITT-analysis a per protocol analysis (PP-analysis) will be performed. This analysis will include only those patients who could be treated with full adherence to the protocol. Besides this, the PP-analysis will parallel the ITT-analysis.

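### Sections 7.1.6, 7.2, 7.4 and 9.1 disagree on how long patients are followed; EFS power depends on the reading, and OS after month 12 is truncated or informatively censored on either one

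*Protocol*

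**What the plan says.** - Protocol 9.1 states the design: "The accrual time will be 24 months with a follow-up time of 12 months (see 7.4"). It continues: "A total of 146 evaluable patients are expected to be sufficient to detect a prolongation of the median EFS from 7 to 11.75 months", at 80% power and α = 0.05. No event target is given.
- Protocol 7.4, to which 9.1 refers, describes the 12 months as the follow-up of the final patient enrolled. Earlier entrants would then be followed for up to 36 months. It gives a total study duration of about 48 months.
- Protocol 7.2 has one follow-up column. It is not restricted to any subgroup, and it runs "until one year after 1st induction therapy". The only column after it is for suspected relapse during treatment or follow-up, which extends nothing.
- Protocol 7.1.6 says that after relapse, study exclusion or refusal of consent, "patients should be followed until one year after the start of the induction therapy".
- The footnote in 7.4 adds treatment failure to that list and names the endpoint: "the patients overall survival will be followed up until one year after the start of the first induction cycle".
- Protocol 9.5 censors event-free patients for EFS at their last follow-up examination. It sets no 12-month limit on EFS or OS.

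**The concern.** Because 9.5 censors EFS at the last examination, the visit schedule decides how many EFS events are seen. A sample size built on 12 to 36 months per patient and a schedule that ends at month 12 cannot both hold. If sites work to 7.2, the confirmatory test has fewer events than planned, and the 11.75-month target median sits at the edge of the observation window. If the one-year stop applies only to the groups in 7.1.6 and the 7.4 footnote, the primary analysis is safe. But patients who have relapsed then leave OS follow-up at month 12 while relapse-free patients stay at risk, so OS censoring depends on prognosis. Events that were never collected cannot be restored by an analysis plan.

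**Working it through.** **Inputs.** Medians 7 and 11.75 months, power 80%, α 0.05 (9.1); the test is done "using two-sided stratified Logrank test" (9.2); patients are randomised "with an equal allocation rate to both treatment arms" (5.1); 146 evaluable and 200 randomised; accrual 24 months. Assumptions: exponential EFS and uniform accrual.

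**Events needed (Schoenfeld).** HR = 7/11.75 = 0.596, ln HR = −0.518. Events = 4(1.960 + 0.842)²/0.518² = 117.0, rounded up to 118.

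**Reproducing 146.** With hazard λ = ln 2/median and follow-up spread uniformly over 12 to 36 months, the event probability is 1 − [exp(−12λ) − exp(−36λ)]/(24λ). This gives 0.884 (control) and 0.736 (temsirolimus), mean 0.810. N = 117.0/0.810 = 144.5, or 73 per arm, hence 146. At 146 patients, 118 events are expected and power is 80.4% (simulated log-rank 80.5%). Other patterns: a fixed 24 months gives N of about 141, close to 146; a fixed 12 months gives about 195. The Freedman formula at 12 to 36 months gives about 151.

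**Reading A: everyone stops at month 12 (7.2 as written).** The event probability is 1 − exp(−12λ), that is 0.695 and 0.507, mean 0.601.

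| Patients informative | Events, 12–36 months | Power | Events, fixed 12 months | Power |
|---|---|---|---|---|
| 146 | 118 | 80% | 88 | 68% |
| 200 | 162 | 91% | 120 | 81% |

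Power is Φ(½·√events·0.518 − 1.960). The simulated log-rank power for 146 patients at a fixed 12 months is 67.8%. If 200 are randomised and 54 are lost at uniform times over windows of 0–3 up to 0–24 months (an assumption), power under the cap is about 70% to 79%.

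The temsirolimus survival at month 12 would be 1 − 0.507 = 0.493. With 73 patients in that arm, the median is not reached if at least 37 are event-free at month 12. The binomial probability of that is about 45%.

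**Reading B: only the groups in 7.1.6 and the 7.4 footnote stop at one year.** Patients who stop because of relapse or failure already have their EFS event, so EFS power stays near 80%. For OS, I simulated the control arm with these assumptions, none of which is in the protocol: 20% of EFS events are deaths; survival after relapse or failure is exponential; OS is censored at month 12 for earlier relapses and at relapse for later ones; all others are followed for 12 to 36 months.

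| Assumed post-relapse median | Kaplan-Meier 24-month OS | True 24-month OS |
|---|---|---|
| 4 months | 0.39 | 0.17 |
| 6 months | 0.45 | 0.24 |
| 9 months | 0.50 | 0.32 |

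The temsirolimus arm is inflated too: 0.60 against 0.39 at a 6-month post-relapse median.

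**The case against.** A reader might infer that the primary test simply has 68% power. The document does not support this as an unconditional statement, for two reasons.

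First, for event-free patients the one-year cap rests on the 7.2 column heading alone, and other text points the other way. Section 7.4 ties the 12 months to the final patient. The limits in 7.1.6 and the 7.4 footnote are conditional, and would be redundant if everyone stopped at one year. The items marked in the 7.2 column largely match those in 7.1.6, so the column may be its tabular form. Section 9.3 counts losses over 24 months, and 146 reproduces at 12 to 36 months. This stands: the planners probably intended the longer follow-up.

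Second, even under the cap, 68% is the lower end. It gives no information to the 54 patients in the attrition allowance, whereas the intention-to-treat rule in 9.2 keeps every randomised patient in the analysis. This stands as well. The 81% upper end, however, needs all 200 to be fully informative, which uses up the whole allowance.

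Three lesser points are also fair. The log-rank test does not need the median to be reached, so the 45% concerns estimation only. The OS figures depend on assumed inputs, concern absolute survival and do not quantify bias in the comparison between arms. OS is secondary. None of this removes the conflict: no visit after month 12 is scheduled for anyone, and the OS problem arises on both readings.

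**Conclusion.** The concern holds as a conflict between sections with conditional consequences. If event-free patients are followed to a common cut-off, EFS power is near 80% as stated. If 7.2 caps them at 12 months, it lies between about 68% (146 informative) and 81% (200 informative). These figures assume exponential EFS at the protocol's medians.

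For OS there is a defect either way. Under a universal cap it is truncated at month 12. Under the conditional stop it is censored in a way that depends on relapse, and it is biased upward whenever relapse raises mortality. The size of that bias rests on assumptions; its direction does not depend on the particular values chosen.

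**What to change.** Reconcile 7.1.6, 7.2, 7.4 and 9.1 around one rule: every randomised patient is followed for EFS status and survival to a single cut-off 12 months after the last patient is randomised, regardless of relapse, treatment failure, transplant or withdrawal from treatment, and as far as consent allows. In 7.2, extend the follow-up column to that cut-off. In 7.1.6 and the 7.4 footnote, replace the one-year limit.

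The cost is a wording change and routine status contacts for earlier enrollees. No extra patients are needed, and the cut-off at 24 + 12 = 36 months fits within the roughly 48 months in 7.4.

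If follow-up is instead to end at 12 months for everyone, state that in 9.1, restate the EFS power for that design (about 68% on 146 evaluable patients, at most about 81% on 200; about 195 evaluable patients would be needed for 80%), and limit OS claims to 12 months.
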